5.2 SECONDARY ENDPOINTS

Table 7. Secondary immunological endpoints

Secondary Endpoint	Outcome	Timepoint (visit)	Population measure	Comparison	Measure of association
i.	Binding antibodies (IgG), BAU/ml	Day-28	GM (95% CI)	Fractional vs. Standard	GMR (95% CI)
ii.	Binding antibodies (IgG), BAU/ml	Month-6	GM (95% CI)	Fractional vs. Standard	GMR (95% CI)
iii.	Binding antibodies (IgG), BAU/ml	Month-12	GM (95% CI)	Fractional vs. Standard	GMR (95% CI)
iv.	ACE2 Binding inhibition* (wild type), %	Day-28	Mean (95% CI)	Fractional vs. Standard	Difference in means (95% CI)
v.	ACE2 Binding inhibition* (wild type), %	Month-6	Mean (95% CI)	Fractional vs. Standard	Difference in means (95% CI)
vi.	ACE2 Binding inhibition* (wild type), %	Month-12	Mean (95% CI)	Fractional vs. Standard	Difference in means (95% CI)
vii.	ACE2 Binding inhibition* (Omicron), %	Day-28	Mean (95% CI)	Fractional vs. Standard	Difference in means (95% CI)
viii.	ACE2 Binding inhibition* (Omicron), %	Month-6	Mean (95% CI)	Fractional vs. Standard	Difference in means (95% CI)
ix.	ACE2 Binding inhibition* (Omicron), %	Month-12	Mean (95% CI)	Fractional vs. Standard	Difference in means (95% CI)
x.	Neutralising antibody (wild type), NT ₅₀	Day-28	GM (95% CI)	Fractional vs. Standard	GMR (95% CI)
xi.	Neutralising antibody (wild type), NT ₅₀	Month-6	GM (95% CI)	Fractional vs. Standard	GMR (95% CI)
xii.	Neutralising antibody (wild type), NT ₅₀	Month-12	GM (95% CI)	Fractional vs. Standard	GMR (95% CI)
xiii.	Neutralising antibody (Delta), NT ₅₀	Day-28	GM (95% CI)	Fractional vs. Standard	GMR (95% CI)
xiv.	Neutralising antibody (Delta), NT ₅₀	Month-6	GM (95% CI)	Fractional vs. Standard	GMR (95% CI)
XV.	Neutralising antibody (Delta), NT ₅₀	Month-12	GM (95% CI)	Fractional	GMR (95% CI)

Protocol Numbers:

81803 (V9), 81800 (V4), BCOV22 (V3)

Statistical Analysis Plan

Page 24 of 52

				vs. Standard		
xvi. Neutralising antibody (Omicron), NT ₅₀ Day-28	Day-28 GM	GM (95% CI)	Fractional	GMR (95% CI)		
		GIVI (95% CI)	vs. Standard			
xvii.	cvii. Neutralising antibody (Omicron), NT ₅₀ Month-6 GM (95% CI)	Month 6	Month-6	GM (95% CI)	Fractional	GMR (95% CI)
XVII.	Neutraining antibody (Officion), N150	WOULTI-6	GIVI (95% CI)	vs. Standard	GIVIN (95% CI)	
xviii.	Neutralising antibody (Omicron), NT ₅₀	Month-12	GM (95% CI)	Fractional	GMR (95% CI)	
Aviii. Neutransing antibody (Neutransing antibody (Officion), NT50	WOTH 12 GIVI (95% CI)	vs. Standard	GIVIN (93% CI)		

All analyses will be conducted separately for the different booster vaccines, amongst all strata combined, and then stratified by the primary series strata (see

Strategy for multiple imputation

Multiple imputation will be done using a multivariate imputation model (MICE) and 50 imputations. Covariates in the imputation model will be the same as those specified for imputation under the hypothetical strategy (Section 6.15.1 Implementation of the Hypothetical Strategy). For the binary seroresponse outcome, binding antibody levels will be imputed (rather than the relative increase from baseline or binary seroresponse), and then seroresponse will be derived using the imputed value/s.

Subgroup analyses and tests for interaction). GM: Geometric mean. GMR: Geometric mean ratio. *Inhibition of binding between the SARS-CoV-2 receptor binding domain and the host-cell ACE2 receptor by neutralising antibody.

5.3 SAFETY ENDPOINTS

Table 8. Safety endpoints

Safety Endpoint	Outcome	Timepoint	Population measure	Comparison	Measure of association
i.	Any# AE to Day 28 (inclusive)*	28 days post- booster	Frequency [N (%)]	Fractional vs. Standard	Descriptive only
ii.	Any# AE to Day 28 (inclusive)* ^ by severity	28 days post- booster	Frequency [N (%)]	Fractional vs. Standard	Descriptive only
iii.	Any# AE to Day 28 (inclusive)* ^ by causality assessment	28 days post- booster	Frequency [N (%)]	Fractional vs. Standard	Descriptive only
iv.	Any AE to Day 28 (inclusive)* by SOC and severity^	28 days post- booster	Frequency [N (%)]	Fractional vs. Standard	Descriptive only
v.	Duration# of AE to Day 28 (inclusive)* by SOC^	28 days post- booster	Median days {25 th – 75 th percentile}, min - max	Fractional vs. Standard	Descriptive only
vi.	Day of AE onset (days post-booster) to Day 28 (inclusive)* by SOC^	28 days post- booster	N by Day	Fractional vs. Standard	Descriptive only
vii.	AE to Day 28 (inclusive)* by Outcome**^	28 days post- booster	Frequency [N (%)]	Fractional vs. Standard	Descriptive only
viii.	Medically attended unsolicited AE to Month-3 visit (inclusive)	90 days post- booster	Frequency [N (%)]	Fractional vs. Standard	Descriptive only
ix.	SAE to study-end by SOC and expectedness ^a	Month-12 visit	Frequency [N (%)]	Fractional vs. Standard	Descriptive only
x.	SAE to study-end by Outcome**^	Month-12 visit	Frequency [N (%)]	Fractional vs. Standard	Descriptive only

[&]quot;The Safety analysis will only include unsolicited adverse events; solicited adverse events are considered in the Reactogenicity analysis. "Adverse events within 28 days inclusive will be considered, rather than all adverse events prior to the Day-28 visit, which can occur between 28- and 35-days post-booster. "Outcome categories are Resolved, Resolved with sequelae, Ongoing, Fatal and Unknown; denominator is the total number of SAEs rather than the number of participants. 'Recurrent events in the same individual will be counted as a single event (using information from the most severe occurrence); all recurrences will be included in the line list of all adverse events. "Event duration of 'Ongoing' adverse events will be the number of days between onset and the last visit.

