	* Subjects and assessors will be bli	nded to the vaccine dose for one week	
	following administration, and labor	atory staff will be blinded to vaccine	
	dose associated with specimens.		
	Primary vaccine	Booster vaccines	
	Sinopharm (BBIBP-CorV ®)	1 Pfizer-BioNTech (BNT162b2, or	
		Comirnaty [®]) Standard dose (30µg)	
	n= 200		
	2 Pfizer-BioNTech (BNT		
	Comirnaty®) Fractional dose		
	(15µg) n= 200		
	AstraZeneca (ChAdOx1-S, or 3 Pfizer-BioNTech (BNT162b2, or		
	/axzevria®) Comirnaty®) Standard dose (30µg)		
	n= 100		
	4 Pfizer-BioNTech (BNT162b2, or		
	Comirnaty®) Fractional dose		
	(15µg) n= 100		
	Sputnik V (Gam-COVID-Vac®) 3 Pfizer-BioNTech (BNT162b2, or		
	Comirnaty®) Standard dose (30µ		
		n= 100	
		4 Pfizer-BioNTech (BNT162b2, or	
		Comirnaty®) Fractional dose	
		(15µg) n= 100	
OBJECTIVES	Primary objectives –		
	• To assess and compare the immune response measured as		
	binding antibodies (IgG ELISA) following fractional versus		
	standard doses of Pfizer vaccine given as single additional dose		
	in adults 18 years and older in Mongolia who have been		
primed through previous vaccination with Astra Zer Sinopharm or Sputnik vaccines. (Timepoint – 28 da		accination with Astra Zeneca,	
		nes. (Timepoint – 28 days post	
	vaccination)		

	 To assess the rate and severity of the reactogenicity within one-week post-booster for each schedule evaluated (Timepoint – daily, for seven days post vaccination) Secondary objectives - (timepoint – 6,12, 18, and 24 months for all) To compare the duration of immunity, both humoral and cellular, over 24 months for fractional vs standard booster doses of the vaccines listed. To evaluate the different priming capacities of Sinopharm, AstraZeneca and Sputnik vaccines. To assess the impact of prior natural exposure on boosting regimens. To evaluate the safety of the booster dose regimens 	
	To evaluate the safety of the booster dose regimens	

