3.2.2 Secondary outcomes

Immunogenicity

Functional antibody – All samples at all timepoints will be assayed using the GenScript cPass

SARS-CoV-2 Neutralization Antibody detection kit for both the Wuhan strain and Omicron variant RBD antigen in Mongolia.

Neutralizing antibody - A fraction of samples (20%) will be assessed using a SARS-CoV-2 microneutralisation assay undertaken at the PDI, Melbourne. Assays will be done at all six timepoints to the Wuhan strain (first generation COVID vaccine) and for 2 Variants of Concern.

Cellular immunity - Cellular immunity will be assessed on a subset of 40% of participants, with samples collected at six timepoints: baseline, 28 days, 6 months, 12 months, 18 months and 24 months post-vaccination as follows:

- *QuantiFERON Human IFN-γ* SARS-CoV-2 (Qiagen) will be performed using heparinised whole blood
- Peripheral blood mononuclear cells (PBMCs) will also be isolated by density gradient centrifugation within 12 hours of collection and stored in liquid nitrogen at MCRI. Assays performed will include IFN-γ Elispot, intracellular cytokine assays (flow cytometry) and multiplex cytokine assays.
- To assess the impact of prior natural exposure on boosting regimens by comparing antibody responses between those who do/don't report a previous COVID infection.

Safety

• All solicited adverse events (AE) will be collected for 7 days, all unsolicited AE will be collected for 28 days, and all medically attended AE will be collected for 3 months. SAE will be collected throughout the follow up period of 24 months.

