4.8 Consent

Informed consent is a process that is initiated prior to the agreement to participate in the trial and continues throughout study participation. Discussion of risks and possible benefits of this vaccination will be provided to the potential participants prior to obtaining informed consent. Trial staff will go through the Informed Consent Form (ICF), which describes in plain language the trial interventions, the study procedures, and the risks and benefits of participation. The ICF will be HREC-approved and the potential participant will be asked to read and review the ICF. The trial staff will then explain the research study further and answer any questions that may arise.

Written documentation of informed consent is required prior to enrolment into the trial. The potential participant will sign and date the final page of the ICF. The trial staff will witness the consent, confirming that the trial has been fully explained and that the participant understands the rationale for the trial and the trial processes. The potential participant will be informed that they are free to withdraw from the trial at any time. A copy of the ICF will be given to the potential participant.

Following or at the 12 month visit, participants will be invited to participate in an extension study with follow-up visits at 18 months and 24 months. They will be asked to sign a new consent form for the extension.

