7.2 Description of procedures

7.2.1 Visit 1 (Day 0)

Informed consent must be signed by both participant and study doctor or nurse.

Participant eligibility must be confirmed prior to randomisation and on the same date as administration of the investigational product.

Eligibility must be confirmed by a study doctor or study nurse. Randomisation must be completed by the unblinded vaccinator who will document the participant's randomisation number on the enrolment log.

Study staff will administer a Visit 1 questionnaire documenting demographic information, height and weight, dates and type of primary COVID-19 vaccine, prior confirmed SARs-Cov-2 infection(s) documented in medical records, any comorbidities and concomitant medication.

The following vital signs will be recorded by a study doctor or study nurse prior to vaccination: temperature, pulse rate, respiratory rate, and blood pressure.

Prior to vaccination, for all participants, 5mL of blood will be collected and processed according to the SOP. CMI participants will have an additional 25ml collected and processed for Quantiferon analysis and PBMC separation and storage.

Following randomisation, the unblinded vaccinator will administer the applicable vaccine to the participant.

Study staff will provide the participant with a hard copy reactogenicity diary card or email them a REDCap survey form. Study staff will instruct the participant on how to complete the diary card for the day of vaccination and seven days following vaccination. Patients who complete a hard copy diary card will be asked to bring it to their day 28 visit so that the information can be entered in the REDCap database.

Study staff will provide the participant with a thermometer and ruler and detailed instructions on how to use these for measuring temperature and potential erythema and induration. Study staff will provide the participant with a schedule of visit appointments and instruct the participant on how to contact the study staff in case of any SAE or symptoms suggestive of COVID-19.

Study staff will keep the participant under observation for minimum 15 minutes and document any immediate adverse events.

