7.2.3 Visit 4 (Day 28)

An in-person visit will be conducted 28 days following vaccination. Participants with hard copy diary cards will be asked to bring the card to this visit for collection. All Unsolicited Adverse Events will be documented. Study staff will also document any new information regarding solicited adverse events with onset up to 7 days following vaccination, such as resolution. The participant will be informed which vaccine dosage they received based on entry into the CRF by the unblinded staff member. For all participants, 5mL of blood will be collected in an SST tube. For participants in the CMI subset, 5mL of blood for Quantiferon test will be collected in a heparinised tube, and 20mL of blood for PBMC will be collected in a heparinised tube. Blood samples will be kept at room temperature and transferred to the laboratory within 3 hours of collection. SST tubes should be kept cold (around 4 degrees) if not transferred within 3 hours.

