7.2.6 Visit 7 (12 Months)

For all participants, 5mL of blood will be collected in an SST tube. For participants in the CMI subset, 5mL of blood for Quantiferon test will be collected in a heparinised tube, and 20mL of blood for PBMC will be collected in a heparinised tube. Blood samples will be kept at room temperature and transferred to the laboratory within 3 hours of collection. SST tubes should be kept cold (around 4 degrees) if not transferred within 3 hours. Participants will be invited to participate for a further 12 months and will be re-consented for Visit 8 and 9. (For those participants who have already attended their 12 month visit, a phone call will be made and consent signed at Visit 8). All participants will receive a gift card for 50.000 Mongolian Tugrik (~14 USD) at 12 months as some visits will be completed at time of extension. An SMS will be sent to participants monthly between Visit 7 and Visit 8 to check for any breakthrough infections and SAEs.

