7.2.7 Visit 8 (18 Months)

For all participants, 5mL of blood will be collected in an SST tube. For participants in the CMI subset, 5mL of blood for Quantiferon test will be collected in a heparinised tube, and 20mL of blood for PBMC will be collected in a heparinised tube. Blood samples will be kept at room temperature and transferred to the laboratory within 3 hours of collection. SST tubes should be kept cold (around 4 degrees) if not transferred within 3 hours. An SMS will be sent to participants monthly between Visit 8 and Visit 9 to check for any breakthrough infections and SAEs. Participants will be asked if they have received another covid vaccine since their last visit.

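### SAP Table 8 ends its study-end SAE summaries at Month 12, so no required by-dose summary covers SAEs in Months 12 to 24 of the Mongolia Trial

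*SAP*

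**What the plan says.** **SAP.** Table 8 (section 5.3) has two SAE endpoints, each compared descriptively between fractional and standard dose. Row ix is "SAE to study-end by SOC and expectedness"; row x gives SAEs by outcome category. Both are labelled as running to study end, and both have the Month-12 visit as timepoint. SAP 3.3 and Table 4 (section 4.2) likewise end SAE collection at 12 months. The denominators differ: row ix is a frequency in participants, while the outcome breakdown in row x uses the total number of SAEs (Table 8 footnote, repeated under Dummy Table S 3). The page header shows that the SAP covers protocol 81800 V4.

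**Protocol.** The synopsis times all secondary objectives, safety included, at "6,12, 18, and 24 months for all". Section 3.2.2 states that "SAE will be collected throughout the follow up period of 24 months". Texts go out "monthly between Visit 7 and Visit 8 to check for any breakthrough infections and SAEs" (section 7.2.6) and again "monthly between Visit 8 and Visit 9 to check for any breakthrough infections and SAEs" (section 7.2.7). From Day 0, staff also "instruct the participant on how to contact the study staff in case of any SAE" (section 7.2.1). The second year is open only to participants who agree to it: "They will be asked to sign a new consent form for the extension" (section 4.8). By then they know their dose, because at Day 28 "The participant will be informed which vaccine dosage they received" (section 7.2.3).

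**The concern.** Evaluating the safety of the dose regimens is a secondary objective, and the protocol carries it to 24 months. If the SAP is followed literally, the number reported per dose as SAEs to study end is a first-year number. A reader of the final report could take it for the whole follow-up.

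Replacing 12 by 24 in the timepoint column would not settle row ix. Year 2 contains only those who re-consent, and they do so knowing their dose. If uptake of the extension differed between doses, a percentage of all randomised participants at Month 24 would mix SAE frequency with length of observation. Row x does not have this problem, since its denominator is SAEs and not people.

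**Working it through.** The plan gives no SAE rate, re-consent rate or SAE-related sample size, so there is no figure to reproduce. The check is a comparison of texts, followed by person-time arithmetic under stated assumptions.

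**Is there a by-dose SAE summary after Month 12 anywhere?**

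- SAP 6.17 requires separate reporting by dose for the endpoints of section 5.3. For SAEs these are rows ix and x, which end at Month 12.
- SAP 6.2 and 6.4 schedule analyses at Day 28, Month 6 and Month 12 only.
- Dummy Table S 3 has standard and fractional columns for SAEs to study end but names no month. Tables 4 and 8 supply the month, and it is 12.
- The line list in SAP 6.17 has no cut-off and is arranged by allocation, but it is a listing.
- SAP 6.1.8 permits extra descriptive statistics in the study report. It does not require any.
- Protocol 11.3 gives no SAE analysis and leaves detail to the SAP.

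So no required summary exists.

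**How much follow-up is outside rows ix and x?** Per extension participant: (24 − 12)/24 = 50%. Per arm, take 400 randomised (SAP 3.3) and assume no first-year dropout and a re-consent share r:

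- Year 1 = 400 × 1 = 400 person-years
- Year 2 = 400 × r person-years
- Share outside = 400r/(400 + 400r)

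| r (assumed) | Year-2 person-years per arm | Share outside |
|---|---|---|
| 50% | 200 | 200/600 = 33.3% |
| 60% | 240 | 240/640 = 37.5% |
| 80% | 320 | 320/720 = 44.4% |
| 100% | 400 | 400/800 = 50.0% |

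**How many SAEs might that be?** At assumed rates of 0.5 to 5 per 100 person-years, the low end is 200 × 0.005 = 1 per arm and the high end is 400 × 0.05 = 20 per arm.

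**Does the denominator matter for row ix?** Assume the same rate, 2 per 100 person-years, in both arms, with 60% re-consent in one and 80% in the other. For simplicity, count every SAE once.

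- 60%: (400 + 240) × 0.02 = 12.8 SAEs; 12.8/400 = 3.2 per 100 randomised
- 80%: (400 + 320) × 0.02 = 14.4 SAEs; 14.4/400 = 3.6 per 100 randomised

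The crude ratio is 3.2/3.6 = 0.89 although the underlying rates are equal. The absolute gap is 14.4 − 12.8 = 1.6 SAEs per 400.

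**The case against.** The strongest reply is that the SAP matches the protocol version it names. It was written for V4, and SAP 2.4 gives the secondary immunogenicity objective as running over 12 months, in what it says is the protocols' wording. A reader might infer from the silence of SAP 6.1.1 (its list of changes from the protocols) that a known departure was left out. The documents do not support that: on this evidence there was probably no difference to list at the time. The explanation is sound, but the gap remains, because the SAP does not match the protocol now in force.

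A reader might also infer that second-year SAEs would go unmonitored or vanish from all output. That is too strong. The DSMB reviews SAEs at least every six months (Protocol 10.1.3), Protocol 8.6 requires an annual safety report, the line list has no end date, and SAP 6.1.8 leaves room for a further descriptive table. None of these is a required summary by dose, but together they confine the issue to planned reporting.

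Two further points stand. The same lag affects the Month-18 and Month-24 immunogenicity analyses and breakthrough infection, so the SAE rows are best amended together with those. And the re-consent argument concerns how a Month-24 figure should be built, not an error in the present plan; nothing in the documents shows that uptake will differ by dose.

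**Conclusion.** The point holds as a mismatch in planned reporting. Rows ix and x end at Month 12 under a study-end label, while the protocol collects SAEs, and times the safety objective, to Month 24. The size that follows from the documents alone is 12 of 24 months for each extension participant. The 33% to 50% of person-time and the 1 to 20 SAEs per arm rest on assumed re-consent, assumed SAE rates and no first-year dropout. They show a range and are not estimates. Even the assumed 20-point difference in re-consent shifts the crude figure by only 0.4 per 100 randomised. All safety endpoints are descriptive, so no test, error rate or power is involved. Priority is minor to moderate.

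**What to change.** Amend the SAP for the Mongolia Trial only.

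- **Both rows:** keep the present cut, relabel it *to Month 12*, and add a Month-24 (study-end) cut by dose received.
- **Row ix at Month 24:** give N (%), the number per dose who re-consented, and a rate per 100 person-years. State the censoring rule. Table 16 (SAP 6.18) already censors at the last attended visit, and that approach can be reused where possible, with explicit provision to count SAEs and deaths reported after that visit. Censoring at last contact, including text messages, is an option only if reply dates are recorded; the protocol says messages are sent but not that replies are dated. State also whether the rate counts first or all events, since SAP 6.17 collapses recurrences and Table 16 does not.
- **Row x at Month 24:** extend the window and keep the planned denominator, the total number of SAEs.
- **Alignment:** bring SAP 3.3, Table 4, Dummy Table S 3 and the timing in 6.2 into line.

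The cost is a short amendment and a final safety table issued after Month 24. The protocol already provides for the data collection, so no visits or samples are added. The limit is that any second-year rate describes only those who joined the extension.

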7.2.4 Visit 5 (3 Months)

Study staff will contact the participant by phone and document information on any medically attended AE or SAE.

Study staff will also document any new information regarding unsolicited adverse events with onset up to 28 days following vaccination, such as resolution.

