8.2 Capturing and eliciting adverse event/reaction information

Participants will be asked to record local and systemic AEs for 7 days (and longer if symptoms persist at day seven, until resolution or stabilisation) following vaccination in the electronic or paper diary card (solicited AEs). Unsolicited AEs All local and systemic AEs occurring in the 28 days following vaccination

observed by the Investigator or reported by the participant, whether or not attributed to study medication, will also be recorded in participant diary and CRF.

Serious adverse events (SAE's) will be followed up for the duration of the trial. Adverse events of special interest will be categorised as per CEPI guidelines (1).

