6.2 TIMING OF ANALYSES

Due to the rapidly evolving nature of the pandemic, analyses will be conducted for each immunological endpoint once the necessary data have been cleaned and locked, which will be as soon as is practicable after all participants have completed their Day-28 visit (for Day-28 endpoints), Month-6 visit (for Month-6 endpoints), or Month-12 visit (for Month-12 endpoints). Necessary data includes those required for the reactogenicity, safety, and breakthrough infection endpoints, and data on intercurrent events, to the same timepoint as for the immunological endpoint that is to be analysed, as these are essential for interpretation. A list of necessary variables is provided in Section 6.3.

For primary endpoint (i) (comparison of binding antibodies at Day-28 between fractional and standard dose groups), it is estimated that the relevant data will be locked within 8 weeks of the final participant completing their Day-28 visit. The statistical analyses will be conducted within 8 weeks of data locking.

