6.8 ADHERENCE AND PROTOCOL DEVIATIONS

Adherence to the intervention is defined as receiving a trial booster vaccination on Day 0. The number and percent of participants who adhered will be presented by study group.

Pre-defined major protocol deviations (with a direct bearing on the primary outcome) are:

- Receiving a 4th dose prior to the Day-28 visit
- Inclusion and randomisation of an ineligible person
- Receiving the wrong trial vaccination
- Day-28 visit occurring outside of the specified time window (between Day 28 and 35 [inclusive], with Day 0 being the day of trial vaccination)

All protocol deviations will be classified as minor or major prior to unblinding. Major protocol deviations are those that are deemed to significantly affect the rights or safety of a trial participant, or the reliability, accuracy, and robustness of the data. The number and percentage of patients with major and minor protocol deviations will be summarised by study group (as per randomisation), with details of type of deviation provided.

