Incidence risk (proportion	n) of at least one solicited emic reaction within 7 days	Proportions will be estimated with 95% Clopper-Pearson binomial confidence intervals using the Ci Stata command.	
		Supplementary analysis: The following reaction-specific descriptive analyses will also be conducted: Number and percentage of individuals with each reaction type, presented in a radial graph (Dummy Figure 3). Number and percentage of participants with each reaction type, by severity grade (Dummy Figure S 3). Distribution of the day of onset for each reaction type Distribution of the duration of each reaction type	

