6.17 ANALYSIS OF SAFETY ENDPOINTS

Analyses for all safety endpoints (5.3 Safety endpoints) will be amongst all randomised participants according to the trial vaccine received (the "Safety Population"). Recurrent events in the same individual will be counted as a single event (using information from the most severe occurrence); all recurrences will be included in the line list of all adverse events. Population measures for all safety endpoints (5.3 Safety endpoints) will be reported separately for standard and fractional dose groups, by trial vaccine. Analyses of all safety endpoints will be descriptive only. Missing data on severity, onset, SOC, causality, SAE outcome, and SAE expectedness will be described by study group.

In addition, a list of all adverse events will be provided by third dose allocation, trial vaccine, and primary series vaccine, including the following parameters:

- the patient identifier
- age
- sex
- weight
- height
- adverse event (reported term, lower-level term, and SOC)
- day of onset (from Day 0)
- days since receipt of 4th COVID-19 vaccine dose (self-initiated or as rescue) (if applicable)
- duration (in days)
- severity grade
- seriousness (serious/non-serious)
- special interest (yes/no)
- expectedness (yes/no)
- action taken
- outcome (Resolved, Resolved with sequelae, Ongoing, Fatal and Unknown)
- causality assessment/relatedness (noting 'adverse reactions' and 'serious adverse reactions')
- concomitant medication at baseline
- concomitant medication during study (prior to event)
- concomitant medication in response to event
- comorbidities at baseline
- brief narrative (SAEs only)

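### Ongoing adverse events are given a completed duration ending at an undefined last visit, although that value is only a lower bound

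*SAP*

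**What the plan says.** SAP 5.3, Table 8, endpoint v is "Duration# of AE to Day 28 (inclusive)* by SOC", reported by arm as median days, 25th to 75th percentile, minimum and maximum. The table notes restrict it to unsolicited events. For events whose outcome is Ongoing, the note says that the duration of such "adverse events will be the number of days between onset and the last visit". Neither document defines *last visit*, and neither censors, flags or sets apart these values in the summary.

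Three other places bear on the reading:

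- **Data cut.** SAP 6.2 requires safety data to be locked "to the same timepoint as for the immunological endpoint that is to be analysed". The lock list in SAP 6.3 names AE outcome but not onset or resolution date.
- **Status updates.** At the Month-3 call, Protocol 7.2.4 says: "Study staff will also document any new information regarding unsolicited adverse events with onset up to 28 days following vaccination, such as resolution". SAP Table 4 also names Month 3 for new information on these events. No later scheduled update of 28-day events is specified.
- **Status of the analysis.** SAP 6.17: "Analyses of all safety endpoints will be descriptive only".

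**The concern.** An event still ongoing when last seen is right-censored: its duration is at least the observed time. The footnote turns that minimum into an observed duration. A plain median and quartiles then mix true durations with follow-up times, and the follow-up times depend on which visit counts as last.

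The SAP handles the same structure properly elsewhere. For the breakthrough-infection rate (Table 16), person-time is censored at the last attended visit.

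At stake is the description of long-lasting events in each dose arm. These are the events most likely to carry an assigned value, and SAP 6.1.2 intends the safety results to be read alongside the immunogenicity results.

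**Working it through.** The plan states no AE duration and no expected share of ongoing events, so there is no figure to reproduce. The check applies the footnote rule and compares it with a Kaplan-Meier (KM) summary.

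**Inputs.** Rule for ongoing events: duration = day of last visit − day of onset (SAP Table 8). Day-28 visit window: "between Day 28 and 35 [inclusive], with Day 0 being the day of trial vaccination" (SAP 6.8). Assumed for calendar months: Month 3 = day 91, Month 6 = day 182, Month 12 = day 365.

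**Step 1: one ongoing event.**

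| Onset | Day 28 | Day 35 | Month 3 | Month 6 | Month 12 |
|---|---|---|---|---|---|
| Day 20 | 28−20 = 8 | 35−20 = 15 | 91−20 = 71 | 182−20 = 162 | 365−20 = 345 |
| Day 27 | 28−27 = 1 | 35−27 = 8 | 91−27 = 64 | 182−27 = 155 | 365−27 = 338 |

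Of the Month-6 and Month-12 values, 182−91 = 91 and 365−91 = 274 days lie after the last scheduled status update.

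**Step 2: an invented cell of ten events.** Seven resolved (2, 3, 4, 5, 6, 8, 12 days) and three ongoing (onset Days 10, 20, 26).

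| Last visit | Assigned values | Plain median [Q1–Q3] | Max | KM median | KM Q3 |
|---|---|---|---|---|---|
| Day 28 | 18, 8, 2 | 5.5 [3.25–8] | 18 | 6 | 12 |
| Month 3 | 81, 71, 65 | 7 [4.25–51.75] | 81 | 6 | not reached |
| Month 12 | 355, 345, 339 | 7 [4.25–257.25] | 355 | 6 | not reached |

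The KM median is the first time at which the curve is at or below 0.5. At the two later visits the curve falls by 0.1 per resolution, touches 0.5 on day 6 and ends at 0.3, so the upper quartile is not reached. The gap between 7 and 6 is only a convention: averaging 6 and 8 gives 7. The median is therefore sound at those visits. The upper quartile and maximum are not, because 51.75 = 12 + 0.75 × (65−12) and 257.25 = 12 + 0.75 × (339−12) are interpolated towards a visit date.

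**Step 3: a cell with half ongoing.** Resolved 2, 3, 4, 5, 6 days; ongoing with onset Days 10, 15, 20, 24, 26. The plain median is 4.5 at Day 28, (6+65)/2 = 35.5 at Month 3 and (6+339)/2 = 172.5 at Month 12. KM gives 6 each time. This is a knife-edge case, since exactly half are ongoing, but it shows that the median can fail in a small cell.

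**Step 4: large-sample check.** Assumed, not from the documents: onset uniform over Days 1 to 28; lognormal durations with log-SD 1; last visit uniform over Days 28 to 35; 200,000 simulated events per row.

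| True median | Ongoing | Footnote median | KM median |
|---|---|---|---|
| 3 | 9% | 2.9 | 3.0 |
| 7 | 26% | 6.1 | 7.0 |
| 14 | 47% | 9.6 | 14.0 |
| 30 | 73% | 13.4 | 30.3 |

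With the last visit at Month 3 or later, at most 18% are ongoing and both methods give the same medians (3.0, 7.0, 14.0, 30.2). The upper quartile is then also close: the worst case is 56.9 against 59.3, at Month 3 with a true median of 30.

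**Reading.** At a Day-28 cut, assigned values fall among the resolved ones and pull the quantiles down. At a late last visit they sit above the resolved ones: the median survives while fewer than half are ongoing and the upper quartile while fewer than about a quarter are, but the maximum is set by a visit date.

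**The case against.** The strongest case against is that little rests on this. The endpoint is descriptive. Counts of Ongoing outcomes are reported separately (endpoint vii, Dummy Table S 3), and the line list in SAP 6.17 shows duration beside outcome, so a careful reader can find the assigned values. If *last visit* means the visit at which the event was last reviewed, the value is already the right censoring time. All of that stands, and it limits the severity. It does not cure the summary itself, which still treats a censoring time as a duration.

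Four stronger readings are tempting but not supported:

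- **That the same event changes value across the Day-28, Month-6 and Month-12 analyses.** Table 8 gives endpoint v one timepoint. Only Table 9, on breakthrough infection, says that the analysis is repeated. The columns in Step 1 are alternative meanings of an undefined term, not successive reported results. At a Day-28 cut, 1 to 8 days is correct follow-up time; the error lies in calling it complete.
- **That nobody checks after Month 3.** Protocol 8.3 asks for AEs to be followed to resolution where possible, and Protocol 7.2.5 adds monthly text messages between Months 6 and 12 that cover AEs. What is missing is a scheduled update of the 28-day events.
- **That the rule biases the dose comparison.** Both arms share one visit schedule. Participants learn their dose at Day 28, but nothing in the documents shows attendance differing by arm.
- **That solicited-reaction durations are cut at Day 7.** The footnote covers unsolicited events only. SAP Table 11 plans the "Distribution of the duration of each reaction type" without stating truncation, and Protocol 8.2 has diary recording continue "and longer if symptoms persist at day seven, until resolution or stabilisation".

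**Conclusion.** The rule is wrong as written, and the point is minor. An ongoing event enters a plain median, quartiles and range as a completed duration whose length is set by an undefined visit. Only ongoing events are affected.

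The size depends on the ongoing share and the data cut, neither of which the documents give. Under the Step 4 assumptions, a Day-28 cut understates a true median of 7, 14 or 30 days as 6.1, 9.6 or 13.4. With follow-up to Month 3 or later and few events ongoing, the median is essentially right. What remains is a maximum driven by visit dates, and an upper quartile or even a median that is unreliable in small SOC cells with a large ongoing share. No test, margin, power figure or primary conclusion depends on it.

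**What to change.** Revise the Table 8 footnote and SAP 6.3:

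1. State the data cut for endpoint v.
2. Treat an ongoing event as right-censored at the last visit or contact, up to that cut, at which its status was recorded.
3. Report the Kaplan-Meier median and quartiles by SOC and arm where estimable, with the number ongoing beside them and the range for resolved events only.
4. Add AE onset and resolution dates to the lock list in SAP 6.3.

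The cost is a short SAP edit and modest code. Protocol 8.3 already has onset date, duration, resolution date and outcome captured. It does not list a date on which ongoing status was last confirmed, so that date would have to come from visit and contact records; whether those are in the locked data should be checked first. The drawback is that quantiles may not be estimable in sparse SOC cells. There, give the number ongoing and list the individual durations, marking the censored ones.
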